The aim of this study is to investigate the effects of combined tDCS and PC on recovery in master male runners following a 10K run. The study also aims to examine whether these interventions can shorten recovery time and prevent performance decline after prolonged and intense exercise.

This study will be conducted as a randomized, controlled, crossover trial using a mixed experimental design. Each participant will undergo four different recovery protocols in a randomized order, with a one-week interval between sessions. Randomization will be performed using Research Randomizer (<https://www.randomizer.org/>), assigning participants to one of four sequences (e.g., B–A–D–C). Participants will be identified only by numerical codes to ensure blinding and maintain confidentiality. Each participant will experience all protocols, allowing within-subject comparisons and minimizing order-related bias.

The four recovery protocols are:

- (A) tDCS group: transcranial direct current stimulation only
- (B) PC group: pneumatic compression only
- (C) tDCS + PC group: simultaneous application of both tDCS and PC
- (D) Control group: passive rest with no intervention

tDCS and PC interventions represent the independent variables, while dependent variables include WBQ, TQR, HRV, Stroop Test, vertical jump, and MVIC with EMG recordings.

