Participants will be 35 male long-distance master runners aged 40–55, residing in Bursa, Turkey, with at least five years of consistent training. They will train five days per week, 90 minutes per day, and must meet aerobic fitness criteria established by the American College of Sports Medicine, completing official 10K race under 50 minutes within last six months and maintain a weekly running volume of 60-80 km. Volunteers will be recruited from the local long-distance running community familiar to the principal investigator, [name]. Participants will be excluded if they have used regular medications within the last six months, consumed stimulants, caffeine, or alcohol within 24 hours prior to testing, smoke, have experienced musculoskeletal injuries in the past six months, are currently undergoing physical therapy, or have neurological conditions such as epilepsy or seizure history, or possess cardiac, brain, or other electronic implants. Additional exclusion criteria include open wounds or dermatological conditions on the head, circulatory disorders such as deep vein thrombosis, peripheral arterial disease, severe varicose veins, or prior exposure to tDCS or PC interventions. Participants may withdraw voluntarily, fail to attend sessions, or be removed if cardiovascular, neurological, or orthopedic complications occur during exercise or interventions, or if they experience excessive discomfort or adverse effects from the tDCS or PC procedures. Written informed consent will be obtained after explaining the study's purpose, procedures, potential risks, and benefits. Sample size was calculated using G*Power 3.1.9.7 for repeated measures ANOVA with within-between interaction, effect size $f = 0.30$, $\alpha = 0.05$, power = 0.80, resulting in $n = 28$. Accounting for potential dropouts, 35 participants will be recruited.

Screening and Familiarization Session:

Participants will undergo anthropometric measurements (weight, body fat, height) using Tanita BC 418 MA and Seca stadiometer. Physical fitness will be evaluated with a 12-minute Cooper Test on a 400 m track under controlled conditions (temperature 20–24°C, relative

humidity 50–70%, wind \leq 10 km/h). A 20-minute warm-up including jogging, accelerations, jumps, and stretching will precede testing. Distances will be recorded with a Polar V3 GPS watch.

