Participants will also complete a familiarization session with the 10K course, tDCS and PC devices, Stroop Test, MVIC, and vertical jump measurements to ensure procedural understanding.

Experimental Sessions

Pre-run Measurements (T1): Immediately prior to the 10K run, participants will complete the TQR, and the WBQ in the gym. Following this, the Polar Vantage V3 GPS-enabled watch and H10 heart rate strap will be fitted to each participant, and HRV data will be recorded for 5 minutes in a seated position.

After HRV recording, participants will perform the Stroop test under researcher supervision using a computer. Subsequently, vertical jump performance will be assessed. Participants will start from an upright standing position, perform a preliminary downward squat by flexing the knees and hips, and immediately extend the knees and hips to jump vertically. Vertical jump measurements will be performed three times with a 1-minute interval between trials, and the results will be recorded.

Following the jump assessment, participants will be fitted with an EMG device for the MVIC test. EMG signals will be recorded from the Vastus Lateralis, Rectus Femoris, and Vastus Medialis muscles during the test.

10K Run: After Test-1, participants will complete a 10K run on the athletics track at Bursa Uludağ University (BUU). The route begins and ends at the Faculty of Sports Sciences, BUÜ. Participants will have 30 minutes for individual warm-up and preparation.

The run will be performed at 75% intensity, determined using the Karvonen method, based on each participant's maximum heart rate obtained during an on-field Cooper test. Target heart rate zones will be set with a ± 5 bpm tolerance. GPS and HRV tracking will be conducted using the Polar Vantage V3 watch. Additionally, perceived exertion will be assessed verbally using the Borg-20 scale at the 5K mark and immediately after completing the run, with responses recorded by the researchers.

Post-run Measurements (T2): Immediately after completing the 10K run, the procedures conducted in Test 1 will be repeated.

Interventions:

Participants will be randomly assigned to one of four protocols:

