- **(D) Control:** Participants in the control group will be positioned in a semi-recumbent posture at approximately 45° recline for 20 minutes without receiving any intervention. During this period, participants will remain passive in a quiet, distraction-free environment. The 45° semi-recumbent posture is consistent with the intervention groups to control for physiological variations arising from body positioning (e.g., blood flow, venous return, postural hemodynamic changes). Active recovery strategies (e.g., walking, stretching) were deliberately excluded to avoid potential confounding effects. This standardized passive rest condition allows for a valid comparison of intervention effects between groups.

Post-intervention Measurements (T3): The procedures conducted in Test 1 will be repeated immediately after the participant completes the assigned intervention protocol.

Outcome Measures:

- Subjective scales: Well-being Questionnaire, Total Quality Recovery
- Heart rate variability (HRV) and GPS
- Cognitive performance via Stroop Test
- Vertical jump height via My Jump app
- MVIC with EMG on quadriceps muscles following SENIAM protocol
- tDCS and PC applied according to standardized protocols

Statistical Analysis

Data will be analyzed with IBM SPSS 29. Normality (Shapiro-Wilk), homogeneity (Levene), and sphericity (Mauchly) will be tested. Two-way repeated measures ANOVA (4 Time \times 4 Group) will assess interactions, with Bonferroni post-hoc tests. Effect sizes will be reported using partial eta squared (η_p^2): small (>0.01), medium (>0.06), large (>0.14). Significance threshold $p < 0.05$.

This study will provide comprehensive insight into the effects of tDCS and PC, alone and in combination, on recovery in older endurance athletes, contributing evidence-based recommendations for optimizing performance and minimizing injury risk.

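### The sample size comes from a within-between routine and the planned ANOVA names a fourth time point, but the crossover compares protocols within runners at three times

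*Combined protocol and SAP*

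**What the plan says.** The Method section calls the study a "randomized, controlled, crossover trial using a mixed experimental design". It says each participant goes through all four protocols, one week apart, in one of four randomised sequences, and that this permits within-subject comparisons.

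The participants paragraph of the same section states: "Sample size was calculated using G*Power 3.1.9.7 for repeated measures ANOVA with within-between interaction". Its inputs are f = 0.30, alpha 0.05 and power 0.80, giving n = 28; 35 will be recruited to allow for dropout. It gives no number of groups, number of measurements, correlation, epsilon or effect-size convention.

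The Statistical Analysis section plans a "Two-way repeated measures ANOVA (4 Time" by "4 Group) will assess interactions, with Bonferroni post-hoc tests". It adds: "Normality (Shapiro-Wilk), homogeneity (Levene), and sphericity (Mauchly) will be tested". It also says: "Effect sizes will be reported using partial eta squared".

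The assessments described are T1 (before the run), T2 (after the run) and T3 (after the intervention). The Research Question names the same three. No fourth is described.

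Two further statements read as if the groups were parallel. Under Interventions: "Participants will be randomly assigned to one of four protocols". The Control item says that the passive-rest condition "allows for a valid comparison of intervention effects between groups".

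**The concern.** A within-between interaction needs a factor that differs between participants. In this crossover the only randomised factor of that kind is sequence, which no hypothesis concerns and the planned analysis does not test. The comparisons in H1 to H3 are made within each runner, so the stated power belongs to a different test.

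The only planned model has four levels of time where the study has three, so it cannot be fitted as written.

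The plan also does not say whether Group is a within- or between-participant factor:

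- **Towards pairing:** the repeated-measures label, Mauchly's test and the reference to within-subject comparisons.
- **Towards independent groups:** the mixed-design label, assignment to one of four protocols, the comparison between groups, Levene's test and the sample-size routine itself.

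An analyst who followed the second set would treat 28 runners as 4 × 28 = 112 independent ones. Leaving that choice until the data are in hand would make the main analysis a post hoc decision.

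**Working it through.** **1. Reproducing n = 28.** From the plan: f = 0.30, alpha 0.05, target power 0.80, and k = 4 groups by m = 4 times. Assumed, because not stated: correlation ρ = 0.5 and epsilon ε = 1. For the within-between interaction (noncentral F),

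λ = f²·N·m/(1 − ρ), df1 = (k − 1)(m − 1), df2 = (N − k)(m − 1).

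- Four times, N = 28: λ = 0.09 × 28 × 4/0.5 = 20.16, df 9 and 72, power 0.863. N = 24 gives 0.782. The smallest N is 25, which becomes 28 when rounded up to equal groups.
- Three times, N = 28: λ = 0.09 × 28 × 3/0.5 = 15.12, df 6 and 48, power 0.789. The smallest N is 29, which becomes 32.

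So 28 matches the routine run with the non-existent fourth time. Other settings also give 28, for example four groups and three times at ρ of about 0.52 to 0.59, or two groups and three times at ρ = 0.3 (power 0.823; 0.790 at 26). Its origin is therefore an inference.

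**2. Power for the test the design supports.** For a 4 × 3 interaction with both factors within-participant, df1 = 6ε and df2 = 6(N − 1)ε. The answer depends on how f is read:

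- Reading A, on the partial-eta-squared scale the plan reports (an assumption): λ = f²·df2. At N = 28 and ε = 1, λ = 0.09 × 162 = 14.58.
- Reading B, against the interaction error SD: λ = f²·12·N·ε. At N = 28 and ε = 1, λ = 0.09 × 12 × 28 = 30.24.

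| ε | A: power at 28 | A: power at 35 | A: smallest N | B: power at 28 |
|---|---|---|---|---|
| 1 | 0.81 | 0.91 | 28 | 0.99 |
| 0.75 | 0.72 | 0.83 | 33 | 0.97 |
| 0.5 | 0.59 | 0.70 | 43 | 0.91 |

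**3. Effect of entering Group as between-participant.** Simulation with 28 runners, four conditions, three times and 30,000 runs per setting; r is the correlation of a runner's changes across sessions. The T3 effect is in the ratio 1 : 0.5 : 0.5 : 0 for combined, tDCS, PC and control, scaled to λ = 14.58 for the paired test at every r.

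| r | Type I error, between entry | Power, between entry | Power, paired test |
|---|---|---|---|
| −0.2 | 0.10 | – | – |
| −0.1 | 0.08 | – | – |
| 0 | 0.05 | 0.82 | 0.81 |
| 0.25 | 0.01 | 0.62 | 0.81 |
| 0.5 | <0.001 | 0.27 | 0.81 |

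The paired test keeps its type I error at about 0.05 throughout.

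**4. What paired contrasts can detect.** Two-sided paired t test (noncentral t, n − 1 df, noncentrality dz·√n), 80% power, where dz is the mean paired difference divided by its SD:

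| Bonferroni family | Alpha per test | dz at 28 | dz at 35 |
|---|---|---|---|
| All six pairs | 0.05/6 = 0.0083 | 0.70 | 0.62 |
| Four pairs | 0.05/4 = 0.0125 | 0.67 | 0.59 |

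In units of the SD of the change, multiply by √(2(1 − r)). For six pairs this gives 0.83, 0.70 and 0.54 at 28, and 0.73, 0.62 and 0.48 at 35, for r = 0.3, 0.5 and 0.7.

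**The case against.** **The paired reading is the likelier one.** The plan says every runner receives every protocol and attaches the word group to each protocol, so Group may only mean condition. The assignment sentence falls within the experimental-session description and can be read per session. All descriptions of the assessments give three, so 3 × 4 can be recovered. This stands as a guess at intent, but the plan does not say it, and several phrases plus the sample-size routine point the other way.

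**The loss of power depends on scaling.** The fall to 0.27 holds the effect fixed relative to the paired test's error, so the raw effect shrinks as r rises. With the raw effect held at its r = 0 size (8,000 runs), between entry has power 0.82/0.80/0.78 at r = 0/0.25/0.5, while the paired test rises to 0.82/0.92/0.99. This is correct. The harm is best read as giving up what the crossover gains; at r = 0 nothing is lost.

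**The time-count error alone is small.** Under the named routine at the assumed settings, power at 28 is 0.789 against 0.80, and the 32 required is below the 35 recruited. That also stands, but it does not make the routine the right one.

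**Keeping 35 is asserted before recalculation.** Under reading A with ε = 0.5, 43 would be needed for 0.80. This limits what may be claimed: 35 can be kept if the plan states what 35 detects, not if it promises 0.80 for f = 0.30 whatever epsilon is.

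Missing period and sequence terms and a missing sphericity correction are separate matters and do not weaken this point.

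**Conclusion.** The concern holds and should be settled before any outcome data are analysed. The stated power belongs to a routine that does not match the comparison of interest, and the only planned model names a time level that does not exist. The plan also leaves pairing open.

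This is a mismatch of design and analysis, not an arithmetic error: 28 reproduces under ordinary settings. Nor is the trial shown to be underpowered. Power at 28 for the within-participant interaction lies anywhere from 0.59 to 0.99 over ε from 0.5 to 1 and the two readings of f, so a reader cannot tell what difference between protocols the trial can detect.

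Losing the pairing is conditional on how Group is entered. Type I error would be inflated only if the across-session correlation were negative; a positive correlation makes the test conservative. The values of ρ, ε and r used here are assumptions, because the documents give none.

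**What to change.** 1. **Statistical Analysis.** Replace the four-by-four specification with one model: 3 Time (T1, T2, T3) × 4 Condition, both within-participant. Drop Levene's test. In the Control item, refer to conditions, not groups.
2. **Method and Interventions.** Delete the word mixed from the design description. Replace the assignment sentence with one saying that every participant receives all four protocols and that their order is randomised.
3. **Sample-size sentence.** Restate it for the within-participant condition-by-time test, or for a paired contrast of a named change, giving the assumed correlation, epsilon and effect-size convention. Possible wording, using T3 minus T2 because the intervention lies between those measurements: *For one outcome, with 28 (35) completers, a two-sided paired comparison of the T3 minus T2 change between two conditions has 80% power for a standardized paired difference of 0.70 (0.62), with Bonferroni adjustment over all six pairs; no adjustment is made across outcomes.* The last clause is a choice the sponsor must confirm, since the plan is silent on it. Use 0.67 (0.59) only if the family is limited to tDCS against control, PC against control, and combined against each single intervention. That assumes control is the comparator for H1 and H2, which name none.

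The cost is wording only, with recruitment kept at 35 (28/0.8 = 35, so 28 completers corresponds to 20% dropout). The stated power becomes specific to one contrast and one outcome. It may look less favourable, particularly for the omnibus test if epsilon is well below 1.

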Study Protocol and Statistical Analysis Plan

Title: The Effects of Combined Transcranial Direct Current Stimulation and Pneumatic Compression on Selected Recovery Parameters After a 10K Run

NCT Number: Pending

Ethics Committee Approval Number: 2025-17/11

Date: 16 December 2025

Objectives and Hypotheses

Research Question:

In this context, the primary research question is:

"How do transcranial direct current stimulation (tDCS), pneumatic compression (PC), and their combined application affect subjective well-being, total quality of recovery (TQR), heart rate variability (HRV), neuromuscular performance (maximal voluntary isometric contraction and vertical jump), and cognitive function (Stroop Test) in master male long-distance runners aged 40–55, immediately before, immediately after a 10-kilometer (10K) run, and following a 20-minute recovery intervention?"

Hypotheses:

- **H1:** tDCS application will significantly improve post-run recovery markers, including subjective well-being, TQR, HRV, neuromuscular performance, and cognitive function.
- **H2:** PC application will significantly improve post-run recovery markers, including subjective well-being, TQR, HRV, neuromuscular performance, and cognitive function.
- **H3:** Combined application of tDCS and PC will produce greater improvements in recovery markers compared to either intervention applied individually.

Objective:

The aim of this study is to evaluate the effects of tDCS, PC, and their combined application on physical, physiological, psychological, and cognitive recovery in master male long-distance runners after a 10K run, with the goal of shortening recovery time and preventing performance decline following intensive exercise.

Specific Aims:

- To investigate the effects of tDCS and PC and combined tDCS+PC on post-run muscle fatigue and neuromuscular performance (maximal voluntary isometric contraction and vertical jump).
- To examine changes in subjective well-being and TQR as indicators of psychological recovery.
- To assess cognitive recovery using the Stroop test.
- To analyze physiological responses by evaluating HRV following each intervention.
- To compare the individual and combined contributions of tDCS and PC to overall recovery.

Method

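### H1 to H3 rest on a Time × Group interaction and an undefined Bonferroni family; five named T3 contrasts, adjusted for same-session T1 and T2, would fit them better at a modest gain in power

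*Combined protocol and SAP*

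**What the plan says.** The Statistical Analysis section holds the whole inferential plan: a two-way repeated measures ANOVA with four levels of Time, in which Time by "4 Group) will assess interactions, with Bonferroni post-hoc tests". No contrast, time point or Bonferroni family is given. Nothing says whether the post-hoc tests depend on a significant interaction, and no covariate is mentioned.

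The design is a crossover: "Each participant will undergo four different recovery protocols in a randomized order, with a one-week interval between sessions". Each session has three described measurement times. T1 precedes the run. T2 follows it: "Immediately after completing the 10K run, the procedures conducted in Test 1 will be repeated". T3 comes after the treatment: "The procedures conducted in Test 1 will be repeated immediately after the participant completes the assigned intervention protocol".

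H1 states that "tDCS application will significantly improve post-run recovery markers", and H2 says the same of PC. H3 states: "Combined application of tDCS and PC will produce greater improvements in recovery markers compared to either intervention applied individually". The last specific aim is "To compare the individual and combined contributions of tDCS and PC to overall recovery". The research question, the objective and the first aim also ask about the combined application in its own right. H1 and H2 name no comparator, but the paragraph on condition (D) Control presents passive rest as the basis for comparing intervention effects.

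**The concern.** The intervention falls between T2 and T3, so T1 and T2 are same-session baselines and only T3 can carry a treatment effect. The interaction asks a broader question: whether the profile over all times differs anywhere among the four conditions. A significant result does not say whether tDCS beats rest, PC beats rest, or the combination beats each single method. Those answers are left to post-hoc tests that the plan does not define.

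Two things are at stake. First, the decision rule for each hypothesis is open, because the text is compatible with very different correction families. Second, T1 and T2 enter only as levels of Time. Post-hoc tests on T3 alone discard them, and change scores give them fixed weights. As covariates, their weights would be estimated from data that are already being collected.

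**Working it through.** **The plan's own figure.** The Method section gives n = 28 from f = 0.30, alpha 0.05 and power 0.80 for a within-between interaction. It does not state the number of groups k, the number of measurements m or the correlation ρ. With λ = f²·N·m/(1−ρ) and df (k−1)(m−1) and (N−k)(m−1):
- k = 4, m = 4, ρ = 0.5: the smallest N is 25, rounded up to 28 for equal groups. At 28, λ = 0.09 × 28 × 4/0.5 = 20.16, df 9 and 72, power 0.863.
- With the three described times (m = 3): λ = 15.12, df 6 and 48, power 0.789 at 28.
- 28/0.80 = 35, the recruitment target.

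So 28 can be reproduced, though not uniquely (k = 2, m = 3, ρ = 0.3 also gives 28). It was sized for an interaction and not for any contrast.

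**What the interaction tests.** With three times it has (3−1)(4−1) = 6 df. Three of them compare the T1-to-T2 change across conditions, before any treatment.

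**What the undefined family means.** Six condition pairs at T3 give alpha 0.05/6 = 0.0083 per test. Six pairs at each of three times give 0.05/18 = 0.0028. All 66 pairs of the 12 cells give 0.00076. Five named contrasts give 0.01.

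**Power for one contrast (A-D).** The documents give no SDs or correlations, so these inputs are assumed: 28 completers, total SD 1, T3 effect d = 0.3 SD, between-session correlation rb = 0.5, within-session correlation rw = 0.5 / 0.7 / 0.8. Session variance is s = rw − rb and residual variance is e = 1 − rw. The variance V of a condition difference, per participant, is:
- T3 alone: 2(s+e) = 1.0 throughout
- T3 − T2: 4e = 2.0 / 1.2 / 0.8
- T3 − mean(T1,T2): 3e = 1.5 / 0.9 / 0.6
- T3 adjusted for T1 and T2: 2[(s+e) − 2s²/(2s+e)] = 1.0 / 0.771 / 0.550 (for rw 0.7: 2[0.5 − 0.08/0.7])

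Power is two-sided noncentral t with noncentrality 0.3·√(28/V), for example 1.587 / 1.807 / 2.141 for the adjusted analysis. The df are 3 × 27 = 81, or 79 with two covariates.

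| Analysis | alpha | rw 0.5 | rw 0.7 | rw 0.8 |
|---|---|---|---|---|
| T3 alone, six pairs | 0.0083 | 0.139 | 0.139 | 0.139 |
| T3 − T2, six pairs | 0.0083 | 0.062 | 0.111 | 0.184 |
| T3 − mean(T1,T2), six pairs | 0.0083 | 0.085 | 0.159 | 0.263 |
| T3 alone, five named | 0.01 | 0.154 | 0.154 | 0.154 |
| Adjusted T3, five named | 0.01 | 0.154 | 0.210 | 0.316 |

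Period terms take 3 more df (76) and, if orders are balanced, lower the last row by no more than 0.001. If the family is 18 tests, T3 alone falls to 0.07.

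**Separating the two sources of gain.** Naming five contrasts instead of six pairs lifts T3 alone from 0.139 to 0.154. At equal alpha (0.05/6), adjusted T3 against T3 − mean(T1,T2) is 0.19 against 0.16 at rw 0.7 and 0.29 against 0.26 at rw 0.8, about 3 points each.

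**When adjustment does not help.** Simulations with estimated slopes and fixed participant effects, at alpha 0.0125, gave for adjusted T3 against T3 alone:
- rb 0.5, rw 0.5: 0.167 against 0.175
- rb 0.7, rw 0.7: 0.303 against 0.313
- rb 0.7, rw 0.8: 0.374 against 0.315
- rb 0.3, rw 0.7: 0.208 against 0.117

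Adjustment gains when values from the same session correlate more strongly than values from different sessions. Otherwise it costs about 1 point.

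**What 28 can detect.** The same formula at alpha 0.01 gives 80% power for A-D at 0.66 / 0.58 / 0.49 SD. An effect of 0.3 SD would need 131 / 102 / 73 completers.

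**The case against.** The strongest reply is that nothing here is an error. Condition order is randomised, the interaction test is valid, and the research question asks about values "immediately before, immediately after a 10-kilometer (10K) run, and following a 20-minute recovery intervention", which a Time × Condition ANOVA describes well. If the post-hoc tests cover all six condition pairs, every contrast needed for H1 to H3 is among them. All of this stands, and it limits the point to efficiency and decision rule.

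Four stronger readings are tempting, but the documents do not support them:
- A reader might infer that the plan would accept H3 whenever the interaction is significant. The plan adds post-hoc tests. On the six-pair T3 reading, if the combination is no better than either single method, both C-A and C-B would come out positive with probability of only about 0.0004. The breadth of the interaction therefore shows no failure of the post-hoc route.
- A reader might infer that T1 and T2 go unused. They are levels of Time in the ANOVA; what is missing is their use as covariates with estimated weights.
- A reader might infer that C-D can be left out because no hypothesis names it. The research question, the objective and the first aim ask about the combined application, so it belongs in the family. Leaving it out would overstate the gain: A-D power at alpha 0.0125 would be 0.173 / 0.234 / 0.345.
- A reader might infer a large gain from adjustment. That depends on the assumed correlations and on the comparison being T3 alone.

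It is also fair to say that Bonferroni over five is conservative, because H3 already requires both C-A and C-B.

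**Conclusion.** The point holds as an efficiency and decision-rule improvement that should be made. The plan does not link any hypothesis to a test, and named T3 contrasts with same-session covariates answer the hypotheses directly from data already collected. The planned analysis is not biased.

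Under the stated assumptions, power for A-D rises from 0.14 (six pairs on T3 alone) to about 0.15 / 0.21 / 0.32. Against six pairs on T3 − mean(T1,T2) the advantage is about 5 to 7 points, part of which comes from the smaller family. Effect size and correlations are all assumed, so the direction is firmer than the size. At 0.3 SD, power stays low under every option. Confidence is medium.

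**What to change.** For each outcome, analyse T3 with condition and period as within-participant factors, participant effects, and T1 and T2 of the same session as covariates. The covariates should act within participants, through fixed participant effects or participant-mean-centred values.

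Name five contrasts and test them whatever the interaction shows:
- A-D for H1
- B-D for H2
- C-A and C-B, both required, for H3
- C-D for the effect of the combined application

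Apply Bonferroni over these five (alpha 0.01 each) and report each contrast with a confidence interval beside partial eta squared. State that passive rest is the comparator read into H1 and H2. Keep the Time × Condition ANOVA as a description of the time course, and reconcile its four levels of Time with T1 to T3.

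The cost is SAP wording, a long-format model in the same software and 2 error df for the covariates, about 1 point of power if the baselines carry no session information. No new data are needed. The change does not deal with multiplicity across the outcomes, and the SAP should note that n = 28 was not sized for these contrasts.

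### Holm's step-down adjustment would serve the post-hoc comparisons at least as well as the named Bonferroni method at the same error rate; the power gained is modest and depends on the family chosen

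*Combined protocol and SAP*

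**What the plan says.** The Statistical Analysis section plans a "Two-way repeated measures ANOVA (4 Time \times 4 Group") in SPSS that "will assess interactions, with Bonferroni post-hoc tests". The criterion is given as "Significance threshold $p < 0.05"; sidedness is not stated. Partial eta squared is to be reported as the effect size. The section does not list the comparisons that the Bonferroni correction covers, mentions no step-down version, and announces no confidence intervals.

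The Method section describes a crossover: "Each participant will undergo four different recovery protocols in a randomized order, with a one-week interval between sessions". The protocols are tDCS (A), PC (B), both together (C) and passive rest (D). H1 reads "tDCS application will significantly improve post-run recovery markers" and H2 reads "PC application will significantly improve post-run recovery markers". H3 expects the combination to do better than either device alone, without saying by how much.

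The sample size is for a "repeated measures ANOVA with within-between interaction", with f = 0.30, alpha = 0.05 and "power = 0.80, resulting in $n = 28", raised to 35 for dropout. No power is given for any pairwise comparison.

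**The concern.** Four protocols give 4 × 3 / 2 = 6 pairs at a time point. Bonferroni in its usual single-step form holds every pair to 0.05/6 = 0.0083, even after the clearest difference has been established. Holm relaxes the threshold after each rejection at no cost in family-wise error. The comparisons likely to benefit are the middle-sized ones: each device against rest (H1, H2) and, if the combination adds something, the combination against each device (H3). A real effect on these would be missed more often than the 5% error rate requires, in a trial whose sample size was not set for them.

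**Working it through.** **The plan's own figure.** G*Power's within-between interaction test uses λ = f²·N·m·ε/(1−ρ), df1 = (k−1)(m−1)ε and df2 = (N−k)(m−1)ε. The documents do not state k, m, ρ or ε. With k = 4 groups, m = 4 measurements, and assumed ρ = 0.5 and ε = 1, N = 28 gives λ = 0.09 × 28 × 4 / 0.5 = 20.16 on 9 and 72 df, and power 0.863. It is the smallest multiple of four to reach 0.80, so n = 28 reproduces. 28/(1 − 0.20) = 35, an implied dropout of 20%. This figure concerns the interaction and says nothing about power for pairs.

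**The two procedures on six pairs.**
- Bonferroni: reject any pair with p ≤ 0.05/6 = 0.0083.
- Holm: order the p-values and compare the k-th smallest with 0.05/(7 − k), that is 0.0083, 0.0100, 0.0125, 0.0167, 0.0250, 0.0500, stopping at the first failure.

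Every Holm threshold is at least the Bonferroni one, so Holm cannot reject less. That is a property of the method and needs no assumption about effects.

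**Simulation inputs.** From the documents: four within-subject conditions, alpha 0.05, 28 completers (or 35). Assumed: a family of the six pairs at T3; two-sided paired t-tests; equal variances and correlations across conditions; effects in units of the SD of a paired difference; and the effect sizes themselves.

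**Power for A versus D at 28 completers** (B versus D agrees within simulation error):

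| Effects for D / A / B / C | Bonferroni | Holm | Gain (points) |
|---|---|---|---|
| 0 / 0.6 / 0.6 / 1.2 (additive) | 0.63 | 0.74 | 11 |
| 0 / 0.5 / 0.5 / 1.0 (additive) | 0.43 | 0.52 | 9 |
| 0 / 0.4 / 0.4 / 0.8 (additive) | 0.25 | 0.31 | 5 |
| 0 / 0.5 / 0.5 / 0.5 (all equal) | 0.43 | 0.46 | 3 |

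Gains are taken from the unrounded values (for example 0.254 to 0.307). In the additive patterns C versus A and C versus B gain as much: 0.63 to 0.74 at effect 0.6. With 35 completers and 0.5/1.0, A versus D goes from 0.56 to 0.67.

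**Error rate.** With no effects, any rejection occurs in about 4.3% of trials under both methods. Across the null and partly null patterns checked, the family-wise error was 0.022 to 0.043 for Bonferroni and 0.039 to 0.045 for Holm. Bonferroni never rejected a pair that Holm retained.

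**The gain in participants.** By the noncentral t at 0.05/6, Bonferroni power rises from 0.436 at 28 to 0.531 at 33 completers (effect 0.5), and from 0.630 to 0.732 (effect 0.6). In those two additive cases Holm is worth about five completers.

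**A wider family.** Suppose the family is the six pairs at each of T1, T2 and T3, 18 in all, with effects at T3 only and time points taken as independent. A versus D then moves from 0.47 to 0.49 (additive 0.6/1.2), 0.29 to 0.30 (0.5/1.0), 0.15 to about 0.15–0.16 (0.4/0.8) and 0.29 to at most 0.30 (all equal at 0.5).

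**The case against.** Bonferroni controls the error rate and biases no estimate, so preferring Holm is a choice between two valid methods. That stands: this is an efficiency point, and a reader who inferred that the plan contains an error here, or that its conclusions would be unsafe, would go beyond the documents.

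The size is also open to challenge. A reader might take 11 points as the loss, or as its upper limit. The documents support neither. The figure needs a family of exactly six pairs, a paired effect near 0.6 and full additivity, none of which is stated; H3 gives a direction only. With other patterns the largest gain on these comparisons runs from about 3 to 6 points when the combination adds little to about 14.5 when it is worth three times one device, and exceeds 20 for some unequal patterns.

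The most substantive objection is that the family is not defined. Post-hoc tests in a time-by-condition analysis may equally compare time points within a protocol. Changing the method while leaving the family open could achieve little: Holm over 18 pairs gives 0.49 where Bonferroni over the six T3 pairs gives 0.63. This stands too, and the fix must therefore list the comparisons.

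Finally, Bonferroni offers simple matching simultaneous intervals and thresholds that do not depend on the other results. This is a real, if small, advantage. The plan announces no such intervals, although in so short a section their absence does not prove that none will be reported.

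**Conclusion.** The point holds as a free or cheap improvement, not as the correction of an error. The direction is certain: on the same family Holm keeps the 0.05 guarantee and never rejects less. The size is conditional. For six pairs at T3 and 28 completers it is about 3 points with equally effective active protocols (paired effect 0.5), and 5 to 11 points with an additive combination and single-device effects of 0.4 to 0.6. It is 2 points or less in the same scenarios if the T1 and T2 pairs are included. Reading A–D and B–D as the tests of H1 and H2 is itself an interpretation, since the plan does not tie its hypotheses to particular comparisons.

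**What to change.** In the Statistical Analysis section, replace the phrase naming Bonferroni with:

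*Holm (step-down Bonferroni) adjustment of the unadjusted paired p-values for the six pairwise condition comparisons at T3, separately for each outcome; any other post-hoc comparisons form a separate Holm-adjusted family.*

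This should be settled before results are seen, because a later switch would look driven by them. It needs no further participants or data. The cost is a few lines of calculation on unadjusted p-values, outside the default SPSS output, and the loss of simple simultaneous confidence intervals that match the tests. If the sponsor does intend to report such intervals, keeping Bonferroni is defensible, but the six T3 comparisons should still be listed as the family.
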